1.1 Purpose of the Study

The overall objective of this study is to test the use of 4 weeks of 24 mg daily ondansetron as compared to placebo on symptoms and brain functioning in patients with obsessive-compulsive disorder (OCD) and tic disorders (TD). This is the second phase (R33 phase) of a 2-phase R21/R33 project. In the first (R21) phase, we found that single doses of 24-mg ondansetron significantly reduced activation of insula and sensorimotor brain regions in healthy volunteers.

Despite extensive research, 30-60% of OCD patients do not respond adequately to first-line treatments (1,2), with similarly disappointing rates in TD3. Treatment presents a particular challenge because these disorders are heterogeneous, with clusters of symptoms likely derived from differing neural etiologies. The Research Domain Criteria (RDoC) approach seeks to address this problem by investigating transdiagnostic components of behavior that more closely align with brain circuitry (4,5). This application focuses on sensory phenomena (SP) as a critical component of both OCD and TD with a discrete neural circuitry centered on the insula and somatosensory cortex. Consistent with the experimental therapeutic approach, the current project will test the ability of ondansetron, a 5-HT3 antagonist acting on sensory pathways, to engage this neural circuitry in order to modulate sensory phenomena.

Sensory phenomena are uncomfortable or aversive sensations that precede compulsions in OCD and tics in TD (6-10). They are highly prevalent, occurring in up to 70% of OCD patients (7-9) and 93% of TD patients (11,12). In the majority of cases, SP may actually drive the repetitive behavior (7,13,14) and are experienced as highly distressing (7,12,13,15), yet these symptoms are not well addressed by standard treatment approaches in OCD or TD (6,16-19). The current project will address this issue by investigating the novel use of ondansetron as a means to target neural systems underlying symptoms of SP. Much research points to a discrete circuit involved in detecting sensory information from the body, with activation of the insula and somatosensory cortex associated with the conscious perception of visceral and somatic sensation (20-25).

Our group (26-28) and others (29-35) have found hyperactivation and hyperconnectivity of insula and somatosensory cortex in OCD and TD. Furthermore, "urges-for-action" – everyday sensory experiences in healthy individuals (such as the urge to blink) that share phenomenological similarity with abnormal urges in OCD and TD – are linked to activation of the insula, somatosensory cortex, and adjacent motor regions (36-40). Taken together, these data provide strong rationale for targeting insula and somatosensory cortex as a means to treat SP in OCD and TD.

FDA-approved for nausea and vomiting (41), ondansetron is a promising novel candidate for the modulation of neural circuits related to SP. Ondansetron has been shown to decrease overall symptom severity in both OCD and TD (42-48), although the neural mechanisms associated with these effects are unknown. Ondansetron is an antagonist at 5-HT3 receptors, which are ligand-gated ion channels located abundantly throughout the peripheral and central nervous system (Wilde & Markham 1996; Ye et al., 2001; Farber et al. 2004; Jakab et al., 2000). The highest density of central nervous system (CNS) 5-HT3 receptors are located in subcortical regions of the interoceptive circuit, including the dorsal horn of the spinal cord, the NTS, and area postrema (Ye et al., 2001; Farber et al., 2004; Bloom & Morales 1998). In addition, 5-HT3 receptors are located in limbic (hippocampus and amygdala) and cortical regions (Jakab & Goldman-Rakic 2000; Bloom & Morales 1998; Tecott et al., 1993; Tuerke et al., 2012), with receptor transcripts identified throughout the cortex including in insula and somatosensory areas (Bloom & Morales 1998; Hawrylycz et al., 2012). Data from the R21 phase showed that single 24 mg doses decreased activity in the insula and somatosensory cortex in healthy subjects, raising the possibility that ondansetron may reduce disorder severity by targeting sensory circuits. Building on these promising findings, this proposal will investigate the effects of 4 weeks of ondansetron on neural targets and SP in a sample of OCD and TD patients.

1.2 Hypotheses

Aim 1 of the study (the R21 phase) has been completed. This application applies only to the R33 phase (Aim 2).

Aim 2 (R33): Further validate neural targets in a sample of OCD and TD patients with sensory phenomena. Employing a placebo-controlled parallel group design, we will measure the effects of 4 weeks of optimal dose ondansetron (that with the greatest effect on neural targets in the R21 phase: 24 mg) on activation and connectivity of insula and somatosensory cortex in patients with at least moderate SP (measured with the Sensory Phenomena Scale7). Hyp. 2: Compared to placebo, ondansetron will be associated with greater decreases in the activation and connectivity of insula and somatosensory cortex from baseline to week 4.

Aim 3 (R33): Examine the relationship between target engagement and clinical symptoms. Hyp. 3a: Compared to placebo, ondansetron will be associated with greater reductions of SP from baseline to week 4, Hyp. 3b: Decreases in overall symptom severity (measured with Y-BOCS and Yale Global Tic Severity Scale) from baseline to week 4 will be mediated by reductions in SP, Hyp. 3c: Decreases in SP between baseline and week 4 will be mediated by reduced activation and connectivity of insula and somatosensory cortex.

1.3 Background

Many psychiatric disorders are associated with altered sensory experiences arising from within the body (Rosario et al, 2009). Examples include increased experience of sensations or urges in muscles, skins, joints or visceral organs in tic disorders, OCD patients with symptoms of "not just right experiences" or disgust sensitivity, and impulse control disorders (ICDs) such as trichotillomania or skin-picking. In OCD, sensory phenomena occur in approximately half of patients, are associated with earlier age of onset (Ferrão et al., 2012), and may be harder to treat with classic cognitive-behavioral approaches to OCD (Summerfeldt, 2004). Of interest, sensory phenomena in OCD are associated with Tourette's syndrome (Ferrão et al., 2012) and respond to pharmacological treatments primarily used for tics (Shavitt et al., 2006). As such, abnormal sensory processing may be a basic mechanism that links various psychiatric disorders.

The process of attending to body sensations is referred to as interoception, and broadly includes the detection of, or attention to, experiences arising from the viscera and soma (Cameron 2001). In healthy individuals, research has revealed a cortical interoceptive network involving insula, anterior cingulate cortex (ACC), and somatomotor cortex (Simmons et al., 2012; Paulus & Stein, 2010; Cameron 2001, Khalsa et al., 2009; Critchley et al., 2004). Furthermore, our group ([name] et al., unpublished data) has obtained pilot data indicating that sensory phenomena in OCD are associated with activity in this interoceptive network (insula and somatosensory cortex).

Ondansetron (OND) is a good candidate for modulation of the interoceptive circuit. It is a selective 5-HT3 (serotonin) receptor antagonist that acts on both peripheral and central receptors (Ye et al., 2006; Haus et al., 2004). OND has long been used to treat nausea and vomiting due to chemotherapy, radiation therapy, anesthesia, and opioid-induced emesis. The mechanism of action of OND for the treatment of nausea is thought to be its action on both peripheral enterochromaffin cells of the intestine as well as on the area postrema (chemoreceptor trigger zone) and the nucleus of the solitary tract (a key node of the interoceptive network). OND has also been used in a variety of conditions other than nausea and vomiting, including irritable bowel syndrome, pruritus, alcohol and substance dependence, and psychosis (Ye et al., 2006; Farber et al., 2004; Haus et al., 2004). Particularly relevant for the current application, OND has been used alone or as adjunctive therapy for the treatment of both OCD and Tourette's disorder, showing some efficacy in small clinical trials (Toren et al., 1999; 2005; Soltani et al., 2010; Hewlett et al., 2003; Pallanti et al., 2009). The mechanisms by which ondansetron improves symptoms in OCD and tic disorders are unknown, but a recent study found that OND application directly into the insula decreased disgust reactions in rats (Tuerke et al.,

2012). These data suggest that ondansetron's clinical efficacy in OCD and tic disorders could be related to effects on interoceptive circuit activity in the insula, a possibility that is being explored in the current protocol.

The current project has two parts (R21 and R33 phases). We completed the first, R21 phase of the project, which was a dose-response investigation of 8, 16, and 24 mg of ondansetron on brain function in healthy volunteers, in May of 2017. From this study, we determined that the optimal dose for modulation of brain circuits of interest is 24 mg. The R33 phase uses a randomized double-blind parallel group design to compare the use of this dose (24 mg) vs. placebo taken daily for 4 weeks to reduce sensory symptoms and alter brain functioning in patients with OCD and tic disorders.

1.3.1 References

For references, please see pages 14-22 in the R21/R33 application.

2 Characteristics of the Research Population

2.1 Number, Gender, Age and Racial/Ethnic Origin of Subjects

2.1.1 Number

It is expected that approximately 45 participants will be enrolled at NYU Langone Medical Center in order to produce 30 eligible participants at this site. Approximately 45 participants will also be enrolled at Nathan Kline Institute to produce 30 evaluable participants at that site. Participants enrolled at NYU will primarily be recruited from flyers throughout the NYU campus, internet advertisements, newspaper advertisements, recruitment emails to university mailing lists and previous studies from prior studies conducted by the lab and will directly contact the Research Coordinator for more information.

2.1.2 Gender

Subjects would include both male and female volunteers.

2.1.3 Age

Subjects will be recruited between the ages of 18 to 60.

2.1.4 Racial/Ethnic Origin

Subjects will be of any racial or ethnic origin.

2.2 Inclusion Criteria

Criteria for all participants

- Ages between 18 and 60 years
- Fluent (speaking and writing) in English.
- Diagnosis of obsessive-compulsive disorder (OCD) or tic disorder (OCD) according to DSM-5 criteria as determined with the Mini International Neuropsychiatric Interview (MINI, Sheehan et al., 1998; J Clin Psychiatry, 59 Suppl 20, 22-33)
- Moderate or greater disorder severity: ≥ 16 on the Yale-Brown Obsessive Compulsive Scale (Y-BOCS) or ≥ 20 on the Yale Global Tic Severity Scale (YGTSS)
- Moderate or greater severity of sensory phenomena (≥ 6 on the Sensory Phenomena Scale, SPS)
- Stable on psychotropic medication for at least 6 weeks or unmedicated.

Additional criteria for all participants who are screened remotely

access to a computer or phone with a camera

2.3 Exclusion Criteria

- Present or previous diagnosis of psychosis, bipolar disorder, or major developmental disorder (autism spectrum disorder with intellectual disability, intellectual developmental disorder) based on DSM-5 criteria
- Present diagnosis of alcohol or substance use disorder (moderate or severe) based on DSM-5 criteria
- Current moderate or higher suicidality as assessed through the C-SSRS with clinician assessment that there is significant risk for the subject if they participate
- Major neurological illness (e.g., self-reported history of organic mental syndromes, head trauma with sequelae, chronic and severe migraines, history of seizures, or other significant medical illness that would make participation unsafe or unfeasible as determined by a licensed clinician on the team)
- Any disability or health problem that prevents them from completing study procedures (e.g. back problems, severe carpal tunnel syndrome, impaired vision that is not corrected with glasses or contact lenses, etc.).
- Pregnant or nursing women
- Positive urine toxicology (except for currently prescribed medications or cannabis) or positive pregnancy test
- MRI contraindications such as claustrophobia, ferrous implants, braces, or pacemakers
- Subjects with a medical condition or other predisposition that increases the risk of adverse effects when taking ondansetron (by self-report or medical clearance testing). These include, but are not limited to, individuals with drug allergies or known hypersensitivity to ondansetron (or other 5-HT3 antagonists), heart disease, congestive heart failure, heart rhythm disorder, congenital long QT syndrome, electrolyte abnormalities (e.g., hypokalemia, hypomagnesemia) or hepatic impairment.
- All subjects will have a thorough review of their medical history and concomitant medications to evaluate for potential interaction effects that may impact serum ondansetron concentrations. Participants felt to be at risk of having a significantly reduced effective serum ondansetron concentration (e.g., due to concomitant carbamazepine or phenytoin) or elevated effective serum ondansetron concentration (e.g. due to liver disease, significant potential P450 isoenzyme inhibitors, or known P450 isoenzyme deficiencies) may be excluded at the determination of the study physician
- Subjects who report taking apomorphine (which is a contraindication to ondansetron)
- Subjects taking a 5-HT3 antagonist (as cross-reactivity with other 5-HT3 antagonists has been reported)
- Subjects with abnormal (with clinical significance) EKG including abnormal QT will either be excluded
 from participation or, if eligibility is unclear, will be referred to a cardiologist for further determination of
 safety for participation. Subjects with QT prolongation (QTc>450 ms for men and >470 ms for women)
 will be excluded.
- Subjects with abnormal liver function, electrolytes, or other lab results (as determined by CBC/CMP) will be excluded from participation if the study team physician determines these abnormalities make it is unsafe for them to participate
- Present diagnosis of Phenylketonuria (PKU).
- Excess ginger consumption (consumption in meal or with supplements > once per week)

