- 2a. Family History Assessment (15-30 minutes): A member of the research team will administer the Family History Questionnaire to the participant. This tool will be used to ask more detailed questions related to family psychiatric and medical history.

3. Medical Screen (30-60 minutes)

Some portions of the medical screen (3a, 3b, 3c) may be performed in a separate in-person visit if the psychiatric and symptom evaluation portion of the screening visit is conducted remotely due to COVID-19 safety concerns. In this case, participants will be transported to Clinical Research Center at Bellevue Hospital or the NKI Outpatient Clinical Research Division (OPRD) using a car service paid for by the study. The participant may drive themselves if they have a car available. A researcher will ask questions about the participant's recent medical history, including inquiring about any surgeries, hospitalizations, or significant illness. This will include over-the-counter commercially-available urine drug and pregnancy tests purchased from Fisher Scientific or other approved vendors. Questions will again be asked to assess for the presence of exclusionary medical conditions (allergies to ondansetron or other 5-HT3 antagonists, heart disease, congestive heart failure, heart rhythm disorder, congenital Long QT syndrome, electrolyte abnormalities, and hepatic impairment). Any subject meeting these conditions will be excluded from participation (see 3a and b). Additionally, subjects who report taking apomorphine will also be excluded from participating in the study. Those with lab results (see 3a) or EKG abnormalities (see 3b) that would make participation unsafe will be excluded.

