- 3.a. Blood Tests: During the Screening Visit, Complete Blood Count (CBC) and Comprehensive Metabolic Panel (CMP) tests will be run to ensure lack of major medical illness or abnormalities that would increase risk. For participants screened through NYU, these blood tests will be performed at either the Clinical Research Center at Bellevue Hospital through the resources of the CTSI or the blood will be collected by a nurse practitioner at NYU Langone Medical Center ([name]) and processed at Clinical Laboratories, located at Tisch Hospital. Subjects undergoing medical procedures at NKI will have blood drawn and processed through the NKI Outpatient Clinical Research Division. Subjects with electrolyte abnormalities, hepatic impairment, or any other major medical illness that would increase risk will be excluded from further participation.
- 3.b. EKG: During the Screening Visit, an EKG will also be performed either at Clinical Research Center at Bellevue Hospital through the CTSI, on the 8th floor of [name] (Psychiatric department testing rooms), or the NKI OPRD, The results from the EKG will be read by a licensed study team physician or nurse practitioner regardless of where the EKG is acquired, to determine that it is safe for the subject to continue in the study. If the EKG results are abnormal, the patient may be referred to a cardiologist for follow-up and a repeat EKG may be conducted. If safety cannot be established, the subject will be excluded from further participation.

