Subjects with QT prolongation will be excluded for safety. For the purposes of the study, QT prolongation is defined as a QTc>450 ms for men and >470 ms for women. Should this be identified at screening, a repeat EKG will be obtained immediately as a confirmation and, if confirmed, the participant will be excluded from the study. If the QTc at screening is greater than 430 but less than 450 for a man or greater than 450 but less than 470 for a woman, we will enroll pending other safety assessments and additionally perform two surveillance EKGs at week 1 and at week 2. While numerous psychotropic medications can prolong QT intervals, we do not determine that a participant being prescribed another medication known to prolong QT intervals prior to enrollment in the study constitutes additional risk assuming the pre-randomization EKG shows no evidence for QT prolongation. Should a participant have, for any clinical reasons, a medication change by their primary clinical outpatient team during the randomization period, this will be reviewed by a study physician and an EKG may be performed, if indicated.

- 3.c. Vital Signs: The medical screening would also involve administering Vital Signs by a licensed CTSI or study team physician or nurse practitioner to ensure safety to participate.
- 3d. Medical history: The coordinator will obtain information regarding the participant's medical history which may involve administering the Patient-Rated Inventory of Side Effects (PRISE). This information will be reviewed by a licensed study clinician and discussed with the participant during a remote meeting between the clinician and the participant via phone or Webex. At that time, and after reviewing results from the bloodwork, EKG, and vital signs, the study clinician will determine whether a physical exam is required to determine safety. If the physical exam is required, it will be conducted during the baseline visit at Nathan Kline Institute, which already requires an in-person visit, prior to randomization.

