6.2 Protection Against Risks

We plan to protect participants from adverse effects of ondansetron by excluding individuals predisposed to risk caused by allergies to ondansetron or other 5-HT3 antagonists, heart disease, congestive heart failure, heart rhythm disorder, congenital Long QT syndrome, known electrolyte imbalance, and hepatic impairment. Additionally, subjects who report taking apomorphine, and pregnant and nursing women will also be excluded. We will assess for the above conditions by evaluating medical history (via self-report during the phone screen and again during the Screening Visit), and conducting pregnancy testing during the Screening Visit. We will obtain a History & Physical, Vital Signs, and EKG during the Screening visit and will exclude for any cardiac abnormalities that the study physician ([name]) judges to pose a safety risk. Complete Blood Count (CBC) and Comprehensive Metabolic Panel (CMP) tests will also be run to ensure lack of major medical illness or abnormalities that would increase risk. We will exclude subjects with electrolyte abnormalities, hepatic impairment, or any other major medical illness that the study physicians believe would increase risk. We will be carefully monitoring the subject during the experiment to ensure that any drug effects experienced are noted and medical intervention provided, if necessary. All side effects will be assessed weekly, and patients will have a surveillance EKG at the week 2 visit. Higher-risk patients (those with normal QTc within the range of 430-450 ms for men and 450-470 ms for women) will have surveillance EKGs at both week 1 and week 2. The EKG, blood testing, and physician meeting conducted at the Screening Visit will be repeated at the Final (exit) Visit and the study coordinator will also call the patients approximately one week after the Final Visit to ensure safety.

At any point should a medical emergency arise, a study physician or other licensed medical provider will be available. Other facilities at NYU and NKI will be made available if the need arises.

There could be a breach of confidentiality regarding participants study participation or research records, but there are measures in place to limit this risk (see above).

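### Low magnesium is named as a risk condition for ondansetron, but the only screening blood tests the text names are CBC and CMP

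*Combined protocol and SAP*

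**What the plan says.** Section 2.3 (Exclusion Criteria) rules out people with a condition that makes harm from ondansetron more likely. The list gives examples, among them congenital long QT syndrome and "electrolyte abnormalities (e.g., hypokalemia, hypomagnesemia) or hepatic impairment". It accepts two ways of finding these conditions: the participant reports them, or clearance testing shows them.

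A later bullet in Section 2.3 says how laboratory abnormalities are judged: "Subjects with abnormal liver function, electrolytes, or other lab results (as determined by CBC/CMP) will be excluded from participation if the study team physician determines" that taking part would be unsafe.

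The procedures repeat both routes. In Section 4.1, item 3 (Medical Screen) says "Questions will again be asked to assess for the presence of exclusionary medical conditions", and electrolyte abnormalities are on that list. Item 3.a (Blood Tests) says "Complete Blood Count (CBC) and Comprehensive Metabolic Panel (CMP) tests will be run to ensure lack of major medical illness". Section 6.2 (Protection Against Risks) describes the excluded conditions as including "congenital Long QT syndrome, known electrolyte imbalance, and hepatic impairment". It continues: "We will assess for the above conditions by evaluating medical history (via self-report during the phone screen and again during the Screening Visit". It then adds that "Complete Blood Count (CBC) and Comprehensive Metabolic Panel (CMP) tests will also be run".

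**The concern.** The protocol gives two examples of an electrolyte abnormality that matters for the study drug: low potassium and low magnesium. For magnesium, no blood test is named. That leaves self-report, and a person who does not know of a low level cannot report it. Screening is the point at which a low level could be found before the first dose.

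Three features of the trial give this some weight. Section 6.1 says that, to the investigators' knowledge, no earlier study gave single 24 mg doses over several weeks. It also says that adverse effects depend on dose and are more marked with repeated dosing. And Section 4.1, item 3.b, admits people already taking other QT-prolonging drugs if the pre-randomization EKG is clear.

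**Working it through.** The plan gives no figure to reproduce. The check is whether a named exclusion has a named means of detection.

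1. **Condition to be found.** Section 2.3 names low magnesium as an example. Magnesium is mentioned nowhere else in the text.

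2. **Self-report route.** The phone screen, the Medical Screen questions in Section 4.1 and the history-taking in Section 6.2 can find a case the participant knows about. Section 6.2 itself speaks of a known imbalance. An unrecognised case is not found this way.

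3. **Laboratory route.** The screening blood tests are named in three places, and they agree:
   - Section 2.3, laboratory bullet: CBC/CMP.
   - Section 4.1, item 3.a: CBC and CMP.
   - Section 6.2: CBC and CMP.

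   Item 3.a goes on to exclude people with electrolyte abnormalities after testing, so the protocol does intend to find such cases in the laboratory. Whether it finds low magnesium depends on what the CMP measures, which the documents do not say. If the panel omits magnesium (the assumption here), an unrecognised case passes. If it includes magnesium, the case is found and only the wording is incomplete.

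4. **EKG route.** QTc above 450 ms (men) or 470 ms (women) excludes. Those at 430–450 ms or 450–470 ms get extra EKGs at weeks 1 and 2. Everyone has an EKG at the Mid-Trial and Final Visits. These measure QT, not magnesium. For participants outside the borderline group, the first scheduled EKG on drug is at the Mid-Trial Visit: 14 ± 7, or day 7 to day 21.

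5. **Later blood tests.** Section 4.1 describes repeat bloodwork at the Final Visit: 28 ± 7, or day 21 to day 35. Section 4.2 mentions EKG and blood tests for the Mid-Trial and Final Visits together, although the Mid-Trial description in Section 4.1 names only an EKG. Either draw comes after dosing has begun, and no analytes are listed.

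6. **Numbers.** From Section 2.1.1:
   - Enrolled: 45 + 45 = 90.
   - Eligible or evaluable: 30 + 30 = 60.
   - On ondansetron, assuming 1:1 allocation: 60 / 2 = 30.
   - Screening assays: about 90. If the Final Visit repeats the test: 90 + 60 = 150 at most.

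   The documents give no rate of low magnesium, so no expected number of affected participants is calculated.

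**The case against.** The strongest reply is that the gap depends on something the documents do not state. No section lists the CMP analytes, and the schedule-of-events table is not reproduced in the text reviewed. A magnesium test could be in either. This stands as a limit. Against it, the three places that name the tests agree with each other, and a CMP in its usual sense is a fair working assumption.

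A second reply is that there is no contradiction. Low magnesium is only an example, self-report is an accepted route, and other items in the list, such as drug allergy, have no dedicated test. This is right as far as it goes. A reader might infer that the protocol breaks its own exclusion rule, but the text does not support that: a known case can still be excluded. What remains is the unrecognised case. It matters because the protocol looks for electrolyte abnormalities by blood test and names no test for one of its two examples.

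A third reply is that the cardiac risk is watched directly, through the QTc limits, the confirmatory and repeat EKGs, the exclusion of heart disease and rhythm disorders, and physician review at the Mid-Trial and Final Visits. Section 6.1 also cites studies of 24 mg a day for up to 4 weeks with no safety concern beyond mild effects, though typically in divided doses. The data safety monitoring board approved the R33 procedures. All of this lowers the stakes. It does not detect low magnesium, and the protocol lists electrolyte and EKG exclusions separately, so it does not treat one as standing in for the other.

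**Conclusion.** The concern holds as a modest safety gap that is cheap to close. It rests on two assumptions: that the CMP is a standard panel without magnesium, and that the schedule of events adds no magnesium test. Under both, a participant with an unrecognised low level would pass screening and, if allocated to ondansetron, start 24 mg daily. About 30 participants would take the drug, with 1:1 allocation assumed. If either assumption fails, what is left is a sentence of clarification.

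A reader might go further and infer a likely number of exposed participants, or a likely number of cardiac events. The documents support neither. They give no rate of low magnesium and no risk of harm from it at this dose, and they do not explicitly link magnesium to QT; the two only share a bullet. Any probability would come entirely from the rate assumed.

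**What to change.** In the laboratory bullet of Section 2.3, in Section 4.1 item 3.a and in Section 6.2, change the screening bloods to CBC, CMP and serum magnesium, taken from the existing draw. If the panel in use already includes magnesium, say so in those three places. Either way, the explicit wording makes testing uniform, since item 3.a has blood processed at different laboratories for the two sites.

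Send an abnormal result to the study physician under the existing safety rule in Section 2.3, before randomization. Section 4.1, item 3d, already provides a suitable moment: "after reviewing results from the bloodwork, EKG, and vital signs, the study clinician will determine whether a physical exam is required". The exclusion of known conditions in Section 2.3 can stay as it is.

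The cost is about 90 inexpensive assays, or up to about 150 if the test is repeated at the Final Visit. No extra visit or needle stick is needed. The downside is possibly a few more screen failures, or results needing a physician's decision.
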